6.2 Data sources

The following data sources will be used to address the objectives (detailed in **Table 5**):

- Pharmacy records: intervention arms only, Arms 1-3 (i.e., not SOC arm, Arm 4)
 - Items on Prescribing Checklist, including PEP/PrEP dispensing data, age, sex, marital/relationship status, behaviors associated with HIV risk, HIV test result
 - Other services/products purchased
- Clinic records: SOC arm only
 - Items on the Clinical Encounter Form akin to those in the study's Prescribing Checklist
- Brief client surveys: all arms
 - Brief demographics
 - Whether the participant initiated PrEP and/or PEP and, if so, where
 - Whether the participant has refilled PrEP and, if so, where
 - Whether the participant is still taking PrEP/PEP as of today
 - If the participant is still taking PrEP/PEP, how many PrEP/PEP pills they swallowed in the past 7 days
 - PrEP adherence
 - Select HIV risk behavior questions

- Extended client survey: all arms
 - Extended demographics
 - Alcohol use
 - Sexual and mental health
 - HIV risk behaviors
 - Fertility
 - Social harm
 - Acceptability of pharmacy model in which they received PrEP/PEP services
 - Quality of care perceptions Fidelity of services received
 - Willingness to pay
- Provider surveys: all arms
 - Provider demographics
 - Acceptability of pharmacy-delivered PrEP/PEP
 - Feasibility of pharmacy-delivered PrEP/PEP
 - Self-efficacy to delivery PrEP/PEP services at pharmacies
 - Organizational Readiness for Change (ORIC)
 - Willingness to charge
- Client in-depth interviews: all arms
 - Model acceptability
 - Model appropriateness
 - Acceptability of modifications
 - Appropriateness of modifications
- Provider in-depth interviews: all arms
 - Acceptability
 - Feasibility
- Technical assistance (TA) reports
 - Adaptations

Data from the Maisha Meds application on PrEP/PEP delivery/dispensing, survey data, audio files from interviews, and interview transcripts will be stored on secure electronic platforms that meet all data security requirements (e.g., REDCap, Dedoose). Table 5 below summarizes the outcomes and data sources.

Table 5. Data sources

PRIMARY/ SECONDARY	OUTCOME	TIMING	DATA SOURCE
Primary	PrEP initiation	By 60 days	Brief client survey Pharmacy records* Clinic records*
	PrEP continuation	By 60 days	
Secondary	PrEP initiation	By 270 days	
	Any PrEP continuation	By 270 days	
	At least 2 PrEP refills	By 270 days	
	Any stopping and restarting PrEP (i.e., PrEP reinitiation)	By 60 and 270 days	

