We will estimate the ratio of PrEP initiation rates (number of initiations per clients served at the pharmacy, accounting for pharmacy volume over the implementation period) comparing each intervention arm to the SOC arm using a Poisson generalized linear model with log link and robust standard errors. The model will allow for overdispersion to account for increased variability in rates. The outcome will be number of self-reported PrEP initiations from the 60-day brief client survey in each pharmacy. A cluster-level analysis was chosen for the outcome of PrEP initiation because the number of individuals enrolling in the study at a given pharmacy was found to be heavily dependent upon the study arm of the pharmacy. Thus, the available denominator for the individual-level PrEP initiation outcome, number of individuals enrolled in the study, was a poor proxy for the quantity of interest, number of pharmacy PrEP candidates (i.e., individuals determined at risk of HIV acquisition who meet the pharmacy PrEP prescribing checklist criteria). Instead, we will pursue a cluster-level analysis where the outcome is number of initiations at each pharmacy and we account for pharmacy volume as a way to make fair comparisons across pharmacies.

The model will include study arm as a four-level categorical (nominal) variable and a continuous offset variable reflecting pharmacy volume (number of clients per unit time). Pharmacy volume will be measured as the number of transactions per month. Estimates of monthly volume will be obtained up to three times in each pharmacy during the course of the study (to account for seasonal variations); missing observations will be imputed, and we will take the average of the three assessments. To account for the stratified randomization procedure, we will adjust for county as a categorical (nominal) variable. As noted in Section 6.7, our missing imputation strategy (i.e., imputing missing outcome data as failures) will not affect the primary analysis of the pharmacy-level count data and will only influence the secondary analysis described in Section 7.5.1.3.

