7.7 Post-unblinding update: December 16, 2025

The study team was unblinded to the results of the analysis on November 6, 2025 prior to the final DSMB meeting on November 13, 2025. The last version of this SAP, with all sections finalized with the exception of this post-unblinding update, was on November 5, 2025—prior to unblinding of any study team members. Summary statistics generated for the November DSMB meeting showed notable variability in completion of 60-day surveys across the 4 study arms. To understand the source of this heterogeneity, pharmacy data for the three intervention (i.e., non-SOC) arms were evaluated. These data indicated that a large number of individuals who did not complete the 60-day survey did in fact initiate/continue PrEP/PEP. This indicated that the planned outcome imputation approach, in which individuals who did not respond to the survey were assumed to have failed (i.e., not initiated/continued PrEP/PEP), likely did not reflect the nature of missingness. Following conversations with DSMB members and other experts, the study team decided to change the imputation approach.

The new imputation approach would impute PrEP/PEP outcomes for individuals who did not complete the survey using the proportion of PrEP/PEP initiations/continuations among individuals in the same pharmacy who did respond to the survey. Thus, if Pharmacy A enrolled 100 participants, 70 of whom responded to the survey and 14 of whom (20%) indicated they had initiated PrEP, then the PrEP initiation outcome for the 30 non-responders would be imputed as a binomial random variable with a success probability of 20%. As indicated above, evaluation of the pharmacy record data in the three intervention (i.e., non-SOC) arms indicated that the proportion of individuals who, per pharmacy records, initiated PrEP (for instance) was similar among those who did and did not complete the survey (42.8% and 40.5%, respectively). Thus, while the analysis based on the imputation procedure proposed in Section 6.7 will be reported in the main results manuscript as the pre-specified analysis, emphasis in that paper will be placed on the results from the analysis using the new imputation approach described in this paragraph, noting that this was not prespecified. We note that the decision to shift focus to this new imputation approach was made prior to seeing the results with the new imputation approach.

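### The imputation emphasised in SAP 7.7 has no reported support in Arm 4 or for continuation, and the number of random draws is left open

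*SAP*

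**What the plan says.** SAP 7.7 replaces missing-as-failure, for emphasis in the main paper, with an imputation "using the proportion of PrEP/PEP initiations/continuations among individuals in the same pharmacy who did respond to the survey". The rule applies in all four arms. In the worked example a pharmacy enrols 100 clients, 70 respond and 14 of them report initiating; "the PrEP initiation outcome for the 30 non-responders would be imputed as a binomial random variable with a success probability of 20" per cent.

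The evidence offered is that "evaluation of the pharmacy record data in the three intervention (i.e., non-SOC) arms indicated" a proportion initiating PrEP that "was similar among those who did and did not complete the survey (42.8% and 40.5%, respectively"). This is one figure for the three arms together, given as an instance, for initiation only. The same section says that the summaries for the monitoring board "showed notable variability in completion of 60-day surveys across the 4 study arms".

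On data sources, SAP 6.2 limits pharmacy records to Arms 1-3 but lists "Clinic records: SOC arm only". SAP 7.5.1.3 plans a descriptive comparison of survey and clinic-record numbers in Arm 4, not split by whether the client answered the survey.

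The pre-specified missing-as-failure analysis will still be reported. SAP 7.5.1.1 says of that rule that it "will not affect the primary analysis of the pharmacy-level count data", and SAP 6.7 calls it equivalent to a complete-case analysis.

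**The concern.** Every primary contrast compares an intervention arm with Arm 4, so an error in the imputed Arm 4 count enters all three rate ratios. Arm 4 also works differently: clients are referred to a clinic, whereas Arms 1-3 dispense at the enrolling pharmacy. Similarity of responders and non-responders in Arms 1-3 therefore cannot simply be carried over. Pooling three arms may also hide differences between them, and nothing is reported for continuation, the other primary outcome.

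The two analyses to be reported treat all non-responders as failures, or all as like responders, in every arm. Neither shows what happens if Arm 4 differs.

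A smaller matter is that 7.7 describes a random draw without giving the number of draws, the seed or a pooling rule.

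**Working it through.** **1. The plan's own figures.** The example reproduces: 14/70 = 20%. The expected imputed count is 30 x 0.20 = 6, so the expected total is 14 + 6 = 20, the same as 14/0.70.

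Table 4 gives 80% power for PrEP initiation, Arm 1 vs Arm 4. With c = 15 pharmacies per arm, Table 3 means m1 = 16.13 and m0 = 10.08, CV = 0.25 and two-sided alpha = 0.05/3 (z = 2.394):

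power = Phi( sqrt[ (c - 1)(m1 - m0)^2 / (m1 + m0 + CV^2(m1^2 + m0^2)) ] - z ) = Phi( sqrt[ 14 x 36.60 / 48.82 ] - 2.394 ) = Phi(0.846) = 80.1%.

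Table 3 and CV 0.25 are therefore used below. The design ratio is 16.13/10.08 = 1.60.

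**2. The Arm 4 assumption.** Let r be the Arm 4 survey response and d the initiation rate of its non-responders relative to its responders. Per enrolled client, the imputation credits the responder rate p, whereas the true mean is p[r + (1 - r)d]. If Arms 1-3 are imputed correctly,

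reported ratio = true ratio x [r + (1 - r)d].

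SAP 4.5 plans r = 0.75. Observed rates by arm are not given, so 0.60 to 0.90 is an assumed range, as is d from 0 to 1.5. The pooled Arms 1-3 figure gives 40.5/42.8 = 0.946.

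| d in Arm 4 | factor, r = 0.60 | factor, r = 0.75 | factor, r = 0.90 | true 1.60 shows as (r = 0.75) |
|---|---|---|---|---|
| 0 | 0.60 | 0.75 | 0.90 | 1.20 |
| 0.5 | 0.80 | 0.875 | 0.95 | 1.40 |
| 0.946 | 0.979 | 0.987 | 0.995 | 1.58 |
| 1 | 1.00 | 1.00 | 1.00 | 1.60 |
| 1.5 | 1.20 | 1.125 | 1.05 | 1.80 |

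**3. Why the range must pass 1.** With Arms 1-3 at 0.946 and 75% response everywhere, corrected/reported = (0.75 + 0.25 x 0.946)/(0.75 + 0.25d). This is 1.315 at d = 0, 0.987 at d = 1 and 0.9865/1.125 = 0.877 at d = 1.5. A table that stopped at d = 1 could lower a reported ratio by about 1.3% at most.

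**4. The pre-specified analysis.** Scoring a non-responder as failure gives the same count as leaving that client out, but the offset is pharmacy volume and stays whole. If non-responders resemble responders, the reported ratio is the true ratio times r1/r0, where r1 and r0 are the response rates in the intervention arm and Arm 4. With assumed rates of 85% and 65% this is 0.85/0.65 = 1.31.

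**5. The draw.** In the example the imputed count has SD sqrt(30 x 0.2 x 0.8) = 2.19 and a 95% range of 2 to 11, so the pharmacy total runs from 16 to 25.

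For Arm 1 vs Arm 4 at 75% response:
- Responders per pharmacy, at the planned 80% initiating PrEP or PEP: 48.13/0.8 = 60.2 and 26.08/0.8 = 32.6.
- Proportion initiating PrEP: 16.13/60.2 = 0.268 and 10.08/32.6 = 0.309.
- Non-responders (responders x 0.25/0.75): 20.05 and 10.87.
- Imputed totals: 16.13/0.75 = 21.5 and 10.08/0.75 = 13.4.
- Draw variance of the log ratio, the sum over arms of n p(1 - p)/(15 x total^2): SD 0.038, and exp(1.96 x 0.038) = 1.08.

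A simulation of 500 trials with 200 seeds each (ratio of mean counts, robust variance, no offset or county term) gave a seed SD of 0.037 against a mean robust SE of 0.140. At the 0.0167 level the verdict was seed-dependent (significant in 5% to 95% of seeds) in 22% of trials at 75% response, 13% at 90% and 35% at 60%. A smaller simulation (100 data sets, 60 seeds) gave 26% at 75%.

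**The case against.** The SAP is open about the change. It labels the new analysis as not prespecified, keeps the pre-specified one, gives its reason, and says that the choice preceded sight of the new results. That stands, but neither reported analysis tests the Arm 4 assumption.

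Several stronger readings are tempting, and the document does not support them:
- *One draw is used.* The text does not say; single or multiple draws both fit it.
- *The assumption was never checked in Arm 4.* All that can be said is that no check is reported.
- *Arm 4 non-responders initiate less often.* Nothing in the SAP fixes the direction. Below d = 1 the intervention effect is understated; above it, overstated.
- *The standard error is too small.* In simulation the robust SE after one draw (0.140) agrees with the empirical SD (0.144).
- *The statements in 6.7 and 7.5.1.1 are false.* For a count, missing-as-failure and complete-case are the same number. What goes unsaid is the effect of unequal response.

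Seed dependence is also modest. It matters mainly for borderline results such as Arm 1 vs Arm 4 initiation; Table 4 gives 100% power for that outcome in Arms 2 and 3.

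**Conclusion.** The concern holds as to support and specification. The emphasised results rest on an assumption for which the SAP reports no evidence in the arm common to all primary contrasts, and none for continuation. At the planned 75% response the possible distortion is a factor of 0.75 to 1.125 over d = 0 to 1.5, in either direction. If Arm 4 behaved like the pooled Arms 1-3 figure, it would be only 0.987. These sizes rest on an assumed response rate and an assumed range for d.

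The unstated number of draws is secondary. If a single draw were used, the Arm 1/Arm 4 ratio would move by about 7-8% either way, and its verdict would depend on the seed in roughly a fifth to a quarter of simulated trials at the design effect.

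**What to change.** Add the following to 7.7, labelled as made after unblinding:

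1. In Arm 4, compare clinic-record initiation and continuation between survey responders and non-responders. Report the Arms 1-3 check separately by arm and for continuation.
2. Add a tipping-point table with the Arm 4 non-responder/responder ratio varied on both sides of 1 (for example 0 to 1.5) and Arms 1-3 at their observed ratios (pooled 0.95).
3. Remove dependence on the seed. Either average many draws under a stated pooling rule, or use the expected count: reported count x enrolled/responders. The expected count keeps the assumption already chosen.
4. Leave the pre-unblinding text of 6.7 and 7.5.1.1 as it is, to preserve the record. Add a note that missing-as-failure equals ignoring non-responders in the count while the volume offset stays whole, so unequal response across arms scales the pre-specified ratio.

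The cost is SAP wording and a few hours of programming on data sources that the trial already lists. Clinic records may be incomplete, so the Arm 4 check is supportive rather than decisive.

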- PrEP continuation: the number of participants at each pharmacy that initiated PrEP at the pharmacy or clinic and returned to the pharmacy or clinic and refilled PrEP **within 60 days** of initial pharmacy-based screening. *Comparisons between intervention arms and the control will rely on self-report from the 60-day client survey, while comparisons between intervention arms will employ pharmacy records.*

Secondary outcomes include those related to PrEP initiation, PrEP continuation, PrEP adherence, PEP initiation, PEP-to-PrEP transition, and repeat PEP use.

- PrEP initiation: the number of participants at each pharmacy that initiated (i.e., were dispensed) PrEP at the pharmacy or clinic **within 270 days** of initial pharmacy-based screening
- PrEP continuation:
 - The number of participants at each pharmacy that initiated PrEP at the pharmacy or clinic and returned to the pharmacy or clinic and refilled PrEP **within 270 days** of initial pharmacy-based screening (regardless of any gaps in pill coverage).
 - The number of participants at each pharmacy that initiated PrEP at the pharmacy or clinic and **refilled PrEP at least twice within 270 days** of initial pharmacy-based screening (regardless of any gaps in pill coverage).
 - The number of participants at each pharmacy that initiated PrEP at the pharmacy or clinic and refilled PrEP more than 7 days after their expected refill date (i.e., stopping and restarting, also referred to as “PrEP reinitiation”) **within 270 days** of initial pharmacy-based screening.
- PrEP adherence: The median adherence score (0-100) among participants at each pharmacy who initiated PrEP at the pharmacy or clinic –using the Wilson et al. scale (2020, *AIDS*)—as measured at **60 days** following initial pharmacy screening.
- PEP initiation: the number of participants at each pharmacy that initiated (i.e., were dispensed) PEP ≥ 1 times at the pharmacy or clinic within 3 days, as measured at **60 days** and **270 days** following initial pharmacy screening.
- PEP-to-PrEP transition: the number of participants at each pharmacy that successfully completed PEP (tested negative or self-reported testing negative for HIV between 28 and 45 days after initiating PEP at the pharmacy) **and** initiated PrEP at the pharmacy or clinic as measured at **60 days** and **270 days** following initial pharmacy screening.

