In particular, to estimate power, it was assumed that the average pharmacy flow was the same across the four arms; there is no a priori reason to assume otherwise. We further assumed a coefficient of variation (CV) of 0.25. The coefficient of variation characterizes the variability in number of PrEP initiations (relative to pharmacy size) across pharmacies. While this is difficult to know ahead of time, it is typically <0.25 (Hayes and Bennett, *IJE*, 1999). A CV of 0.25 would roughly correspond to a situation where, for example, the average number of PrEP initiations was 20/pharmacy, and 95% of pharmacies had between 10 and 30 initiations (assuming equal flow across pharmacies); this seems to be a reasonable degree of variability in our setting. Given that the analyses will include comparisons of Arms 1, 2, and 3 vs. 4, we used a Bonferroni correction to our alpha level (two-sided alpha = 0.05/3) for the PrEP 60-day initiation/continuation outcomes and the combined PrEP/PEP outcomes (primary and key secondary outcomes).

Based on the hypothesized number of PrEP/PEP initiations and continuations in **Table 3**, we estimated the power would be very high for comparing Arms 2 and 3 to Arm 4 for PrEP initiation

and continuation (primary outcomes) and the combined PrEP/PEP initiation and continuation outcomes (key secondary outcomes; **Table 4**). For the Arm 1 vs. Arm 4 comparisons, the power is estimated to be 80% for PrEP initiation (as designed), 100% for the combined PrEP/PEP initiation outcome, and lower for the continuation outcomes.

→ **Primary outcome assessment will be completed after a total of 1,119 PrEP initiations are achieved. A study duration of 20 months of implementation is targeted.**

Table 3: Number of PrEP, PEP, and PrEP/PEP initiations and continuations per pharmacy (k=15/arm, k=60 total) for >80% power in our PrEP outcomes of interest

	1: Client-sustained	2: Implementor-sustained	3: HTS supported	4: Referral (SOC)	TOTAL (across 60 pharms)
PrEP initiations	16.13	22.18	26.21	10.08	1,119
PEP initiations	32	48	64	16	2,400
Total PrEP/PEP initiations	48.13	70.18	90.21	26.08	3,519
PrEP continuations	8.06 (50% of initiations)	15.52 (70% of initiations)	20.97 (80% of initiations)	6.05 (60% of initiations)	759
PEP continuations	4.34 (13.6% of initiations)	9.12 (19.0% of initiations)	13.90 (21.7% of initiations)	2.61 (16.3% of initiations)	450

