7.5.1.3 Secondary Analyses

For the outcome of PrEP continuation at 60 days, we will conduct a **secondary analysis** of the proportion of participants continuing PrEP at 60 days among those who initiated PrEP. In particular, we will estimate the risk difference of PrEP continuation between each intervention arm and the SOC arm using a Poisson generalized estimating equations (GEE) model with identity link and robust standard errors (Pedoza and Truong, BMC Med Res Methodology, 2016). The outcome will be self-reported PrEP continuation from the brief client survey. The model will include study arm as a four-level categorical (nominal) variable and adjust for county to account for the stratified randomization procedure. To account for varying cluster size (number of PrEP initiators), we will use an independent working correlation matrix and weights for cluster size (Wang et al., Contemp Clin Trials, 2022). Missingness will be addressed as described in Section 6.7. In the event that this model does not converge or yields invalid estimates (e.g., risk differences or confidence intervals outside of ± 1), we will instead fit a modified Poisson GEE model—i.e., a GEE with log link and robust standard errors (Yelland et al., AJE, 2011)—to estimate the relative risk comparing each intervention arm to the SOC arm. Importantly, as this analysis is restricted to those who have initiated PrEP, randomization is not maintained. Thus, we would need to adjust for factors related to initiation in order to remove the bias incurred by selecting only those who initiate (Hernan and Hernandez-Diaz, Clin Trials, 2012).

Additionally, **secondary analyses** for PrEP initiation and continuation at 60 days will be conducted to evaluate whether the effect of the intervention differs by urban/rural pharmacy status, location in Western vs. Eastern Kenya, or by the proportion of enrolled individuals who (1) are female or (2) over the age of 25. This will be done by adding two terms to the model described in Section 7.5.1.1: the main effect of the subgroup variable (e.g., percent female) and an interaction between the categorical intervention variable and the subgroup variable. As part of this analysis, we will estimate the intervention effects within each subgroup.

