In addition, **secondary analyses** for both PrEP initiation and PrEP continuation with 60 days among the clients in the three intervention arms will be performed to compare each of the three intervention arms to each other. The approaches will be identical to that described in Sections 7.5.1.1, with the caveat that the outcome (PrEP initiation or PrEP continuation) will be computed from the pharmacy records, which is available for all three intervention arms and will be a more complete data source than the 60-day follow-up survey. Because the pharmacy data precisely reflects the day initiation or refill takes place, the computation will use a cutoff of exactly 60 days from initial pharmacy-based screening.

A **secondary descriptive analysis** will be performed to compare the data on PrEP initiation by 60 days and PrEP continuation by 60 days from the brief clients surveys versus clinic records

among those in the SOC arm (Arm 4). In particular, we will compare the number (1) initiating PrEP within 60 days and (2) continuing PrEP by 60 days between these two data sources. A similar analysis will be performed for the three intervention arms to compare the number of PrEP initiations and continuations based on the brief client surveys versus the pharmacy records.

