Finally, based on discussions regarding the policy impact of the results of this study, the study team decided to include all PrEP initiations, even among those who had previously been dispensed PEP, and vice versa. All of these decisions were made prior to the study team seeing the results with these changes incorporated.

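### Section 7.7 adds PEP-first clients to the PrEP outcomes but leaves the continuation clock at screening, so the secondary continuation proportion in 7.5.1.3 partly measures each arm's PEP/PrEP mix

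*SAP*

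**What the plan says.** Section 7.7 of the SAP records that, after unblinding, "the study team decided to include all PrEP initiations, even among those who had previously been dispensed PEP, and vice versa". It does not restate the definition of PrEP continuation, its time origin or its denominator. It does say that the decision preceded any sight of results with the change in place.

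Section 3 defines primary PrEP continuation as the number of clients per pharmacy who started PrEP, then "returned to the pharmacy or clinic and refilled PrEP within 60 days of initial pharmacy-based screening". The same section defines successful PEP completion, before a move to PrEP, as having "tested negative or self-reported testing negative for HIV between 28 and 45 days after initiating PEP at the pharmacy".

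Three analyses of 60-day continuation matter here:

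- **Primary (7.5.1.2, following 7.5.1.1):** a count per pharmacy with a pharmacy-volume offset, taken from the 60-day survey. Section 7.5.1.1 places no restriction on survey timing.
- **Secondary proportion (7.5.1.3):** a risk difference against SOC in the "proportion of participants continuing PrEP at 60 days among those who initiated PrEP", also from the survey.
- **Secondary comparisons among Arms 1-3 (7.5.1.3):** counts from pharmacy records, where "the computation will use a cutoff of exactly 60 days from initial pharmacy-based screening".

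**The concern.** A PrEP-first client has up to 60 days for a first dispensing and a refill. A PEP-first client who completes PEP as section 3 defines it has used 28 to 45 of those days before PrEP begins. Section 7.7 makes both kinds of client PrEP initiators without moving the clock. By the wording of 7.5.1.3, both then belong in the denominator of the continuation proportion, but with unequal opportunity to enter the numerator.

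The SAP expects PEP-to-PrEP transitions to be most frequent in Arms 3 and 2. The dilution would therefore fall mainly on those arms, and their difference against SOC would shrink for a reason unrelated to how well they keep clients on PrEP. In the records-based comparisons, PEP-first clients can add to an arm's initiation count while few may be able to add to its continuation count. The two outcomes would then respond differently to the same change.

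**Working it through.** **Inputs, all from SAP section 4.5, Table 3 (per pharmacy, Arms 1/2/3/4)**

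- PrEP initiations I: "16.13 22.18 26.21 10.08".
- PrEP continuations C: 8.06, 15.52, 20.97, 6.05.
- PEP continuations T: 4.34, 9.12, 13.90, 2.61. Section 4.5 uses this term for transition from PEP to PrEP.
- 15 pharmacies per arm, CV 0.25, two-sided alpha 0.05/3.

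Table 3 adds T to C to obtain its combined total (for example 8.06 + 4.34 = 12.40). I therefore treat T as clients not already counted in I.

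**Reproducing the plan's figures**

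Totals: 15 × (16.13 + 22.18 + 26.21 + 10.08) = 1,119; 15 × 50.60 = 759; 15 × 29.97 = 449.6, printed as 450.

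Power by the Hayes-Bennett formula for cluster rates, with m1 and m0 the counts per pharmacy:

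power = Φ( √[14(m1 − m0)² / ((m1 + m0) + 0.25²(m1² + m0²))] − 2.394 )

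- Initiation, Arm 1 vs Arm 4: √(512.4/48.82) = 3.240, power 80.1% (Table 4: 80%).
- Continuation, Arm 1 vs Arm 4: √(56.56/20.46) = 1.663, power 23.2% (Table 4: 23%).

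All 12 cells of Table 4 reproduce to within 2 points.

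**Time left for a refill**

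If PEP starts at screening, 60 − 45 = 15 and 60 − 28 = 32 days remain. The SAP gives no length for the first PrEP supply. If it were about 30 days (an assumption), a refill would fall due between day 58 and day 75. Because this is not stated, I vary f, the share of PEP-first clients who refill by the 60-day measurement, and use the same f in every arm.

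**Continuation proportion**

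Planned: C/I. After 7.7: (C + f·T)/(I + T). The denominator grows by T/I = 27/41/53/26%.

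| | Arm 1 | Arm 2 | Arm 3 | Arm 4 |
|---|---|---|---|---|
| Planned | 50% | 70% | 80% | 60% |
| f = 0 | 8.06/20.47 = 39.4% | 15.52/31.30 = 49.6% | 20.97/40.11 = 52.3% | 6.05/12.69 = 47.7% |
| f = 0.5 | 10.23/20.47 = 50.0% | 20.08/31.30 = 64.2% | 27.92/40.11 = 69.6% | 7.355/12.69 = 58.0% |

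| Difference against SOC (points) | Arm 1 | Arm 2 | Arm 3 |
|---|---|---|---|
| Planned | −10 | +10 | +20 |
| f = 0 | −8.3 | +1.9 | +4.6 |
| f = 0.25 | −8.1 | +4.1 | +8.1 |
| f = 0.5 | −8.0 | +6.2 | +11.6 |

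If f instead equals each arm's planned rate C/I, the formula returns C/I and nothing changes.

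**Primary count**

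The numerator C + f·T cannot fall below C. At f = 0 the count ratios against Arm 4 stay at 1.33/2.57/3.47 and power stays at 23/100/100%. Initiation power for Arm 1 vs Arm 4 rises from 80% to about 86% (20.47 vs 12.69 per pharmacy).

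**Records-based counts, Arm 3 vs Arm 1, f = 0**

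- Initiation ratio: 26.21/16.13 = 1.62 becomes 40.11/20.47 = 1.96.
- Continuation ratio: 20.97/8.06 = 2.60, unchanged.

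**The case against.** A reader might infer that the primary continuation result is damaged. It is not. That outcome is a count per pharmacy against volume, and extra initiators cannot reduce it.

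A reader might also apply the exact day-60 cutoff to the comparison with SOC and conclude that the planned differences all but disappear. The SAP does not support that. The exact cutoff governs only the records-based counts in Arms 1-3. The proportion against SOC rests on survey self-report, 7.5.1.3 adds no timing limit to it, and 7.5.1.1 itself recognises that late surveys allow more time to engage with PrEP. Zero refill is therefore one end of a range. Nor do Arms 2 and 3 come out worst: even at zero refill the order is Arm 3, Arm 2, Arm 4, Arm 1, as planned.

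Two further points stand. The day 28-45 window defines PEP completion for the transition outcome and is not a condition for counting a PrEP initiation, so some PEP-first clients may start PrEP earlier and have more time. PEP-first clients also receive credit elsewhere, in the transition outcome and in combined PrEP/PEP continuation.

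Section 7.5.1.3 does warn that restricting to initiators breaks randomization and calls for adjustment for factors related to initiation. It names no factors, so first product is not clearly covered. None of these points removes the unequal refill time within the 7.5.1.3 denominator.

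**Conclusion.** The concern holds for the secondary continuation proportion in 7.5.1.3 and, in a milder form, for the records-based comparisons of Arms 1-3. Followed as written, 7.7 and 7.5.1.3 together give a proportion confounded with each arm's PEP/PrEP mix. With zero to half of PEP-first clients refilling in time, Arm 3 loses 8.4 to 15.4 of its planned 20 points against SOC, and Arm 2 loses 3.8 to 8.1 of its 10. Arm 1's deficit moves by only about 2 points.

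This rests on Table 3's hypothesized counts, on PEP starting at screening, on transitions being additional to Table 3's PrEP initiations, and on a refill share common to all arms. The first-supply length and the actual survey timing would decide where in the range the trial falls. A general statement that the planned differences vanish is not supported.

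**What to change.** In 7.5.1.3, report the 60-day continuation proportion both with and without PEP-first clients, labelled as a post-unblinding addition. Show PEP-first clients also on the 270-day continuation outcome already defined in section 3, where they have time to refill.

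In the records-based comparisons of Arms 1-3, add refill within 60 days of the first PrEP dispensing as a supplementary analysis; the dated pharmacy records allow it. Beside the day-60 continuation counts, note that PEP-first clients had less time to contribute.

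The cost is a few sentences and one split by first product. The PrEP-first proportion will rest on fewer clients. First product is also a post-randomization variable that the arm may affect, so the split is supportive and should not replace the planned analysis.
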